- a. EOT assessments to be performed within 7 days following subject discontinuation from study treatment. Removal of a subject from CMP-001 treatment is defined as the time at which the Investigator decides to discontinue study treatment. If a subject has CMP-001 withheld for more than 3 consecutive doses for any reason during the Q3W dosing period, resumption of treatment must be discussed with the Medical Monitor, otherwise, the subject will be discontinued from study treatment and will have all EOT assessments performed.
- b. The 100DFU is a safety follow-up visit that may be conducted at the study site or via phone. This visit should occur 100 days (+7) after the EOT. NOTE: If a subject's 100DFU, PTFU, and LTSFU visits overlap, then the visits can be combined into 1 study site visit.
- c. Posttreatment follow-up will be conducted Q3mo (± 2 weeks) for all subjects who discontinue study treatment for reasons other than disease progression (either per RECIST v1.1, iRECIST, or clinical PD per Investigator) but have not met criteria for study discontinuation. These subjects should remain on study and receive disease assessments Q3mo, until discontinuation.
- d. LTSFU will be conducted Q3mo (\pm 4 weeks) after the EOT visit or the last disease assessment date in PTFU and may occur via phone.
- e. CMP-001 dosing will begin on W1D1. Weekly dosing: A window of ± 2 days is permitted for CMP-001 dosing from W1D1 to W7D1. The first dose of CMP-001 may be administered SC or IT, at the discretion of the Investigator; all subsequent doses are planned to be administered IT until no injectable lesions remain. Subjects must complete all 7 weekly CMP-001 doses before moving to the Q3W dosing schedule. Q3W dosing (W10D1+): A window of ±3 days is permitted for CMP-001 dosing from W10D1 throughout the study. When nivolumab is permanently discontinued due to an immune related AE, CMP-001 must also be permanently discontinued. Refer to Section 5.3 for Treatment Compliance.
- f. Nivolumab dosing will begin on W1D1 and continue Q3W throughout the study. When CMP-001 injection and nivolumab dosing fall on the same day, CMP-001 injection will be given before nivolumab dosing. Refer to Section 5.1.1 for Nivolumab Dosing.

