Objective responses will be assessed by BICR and Investigator assessment according to RECIST v1.1. Subjects who experience PD according to RECIST v1.1 may continue study treatment at the discretion of the Investigator and will be evaluated by the Investigator according to iRECIST. Disease status will be assessed by computed tomography (CT) or magnetic resonance imaging (MRI) and other appropriate measures beginning predose at Week 13 Day 1 (W13D1) and will be repeated every 9 weeks (eg, W22D1). Responses (CR, PR, immune complete response [iCR], or immune partial response [iPR]) will be confirmed by a follow-up disease assessment performed at least 4 weeks after the initial response date, and at least 2 weeks after the last CMP-001 injection. Disease assessments will continue every 9 weeks while the subject is on treatment. Disease assessments may continue every 12 weeks for subjects with a response lasting more than 1 year. All scans should be performed at least 2 weeks after the most recent CMP-001 IT injection to account for injection-related pseudoprogression. Imaging should not be delayed in cases where treatment is delayed.

Subjects who discontinue study treatment should complete an end of treatment (EOT) visit and 100-day safety follow-up. Subjects who are posttreatment but have not met criteria for study discontinuation should remain on study for posttreatment follow-up (PTFU) and longterm survival follow-up (LTSFU) and receive study evaluations for efficacy according to the Schedule of Assessments (Table 1).

At the end of the treatment period (2 years), the Sponsor will not continue to provide supplied study treatment to subjects/investigators unless the Sponsor chooses to extend the study. The Investigator should ensure that the subjects receive appropriate standard of care to treat the condition under study.

[figure not shown]

Figure 1: CMP-001-010 Study Schema

Abbreviations: 100DFU = 100-Day Follow-up; EOT = End of Treatment; IT = intratumoral; IV = intravenous; LTSFU = long-term survival follow-up; PTFU = posttreatment follow-up; Q3W = every 3 weeks; Q9W = every 9 weeks; Q12W = every 12 weeks; QW = every week.

a. Disease assessments performed predose beginning at W13D1 (-7 days).

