4.5. Treatment Discontinuation

Treatment discontinuation is defined as any subject who stops receiving study treatment and does not restart within 12 weeks. Subjects who permanently discontinue (> 12 weeks) CMP-001 or nivolumab, may not be retreated with the discontinued study treatment in this study.

Study treatment should continue until 1 of the following occurs:

- Unacceptable AE that precludes further study treatment
- 2 years of study treatment
- Progressive disease per RECIST v1.1; continuation of treatment through suspected pseudoprogression is permitted at the Investigator's discretion until confirmed PD per iRECIST
- Upon request of the Sponsor or regulatory agency
- Clinical disease progression in the opinion of the Investigator
- If medically necessary in the opinion of the Investigator

- Subject withdraws consent for treatment (note that a subject who withdraws consent for additional study treatment and procedures but not for antitumor response will continue to be followed)
- Subject becomes pregnant or begins breastfeeding
- Subject is lost to follow-up
- Death
- End of Clinical Trial

Subjects who permanently discontinue treatment with nivolumab due to an immune related AE must also permanently discontinue treatment with CMP-001.

If a subject achieves and maintains a confirmed CR or iCR by investigator review, treatment with CMP-001 or the combination of CMP-001 and nivolumab may be discontinued at the Investigator's discretion once they meet both of the following criteria:

- Subject has been treated with both study treatments for at least 48 weeks
- Subject has received at least 3 doses of both study treatments beyond the date of the initial CR/iCR

Subjects who discontinue study treatment should complete an EOT visit and 100-day safety follow-up assessments per Table 1. Subjects who discontinue study treatment for reasons other than disease progression (either per RECIST v1.1, iRECIST, or clinical PD per Investigator) should remain on study for PTFU (Section 7.8.) and receive disease assessments according to the Schedule of Assessments (Table 1).

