7.8. Posttreatment Follow-up

Subjects who discontinue study treatment and transition into PTFU will continue to have assessments collected per the time points specified in the Schedule of Assessments (Table 1).

VV-RIM-00381493-1.0 Approved - 27 Nov 2024 GMT-5:00

Posttreatment follow-up disease assessments will continue until disease progression, initiation of another cancer treatment, death, loss to follow-up, withdrawal of consent, or End of Clinical Trial.

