Target Lesions	Non-Target Lesions	New Lesions	Response Assessment
CR	CR	No	CR
CR	Non-CR/Non-PD	No	PR
CR	Not Evaluated	No	PR
PR	Non-PD or Not All Evaluated	No	PR
SD	Non-PD or Not All Evaluated	No	SD
Not All Evaluated	Non-PD	No	NE
PD	Any	Yes or No	PD
Any	PD	Yes or No	PD
Any	Any	Yes	PD

Determination of Tumor Response

Abbreviations: CR = complete response; NE = not evaluable; PD = progressive disease; PR = partial response; SD = stable disease.

NOTE: Subjects with a global deterioration of health status, requiring discontinuation of treatment without objective evidence of disease progression at that time, should be reported as "symptomatic deterioration." Every effort should be made to document the objective progression, even after discontinuation of treatment. Conditions that may define "early progression, early death, and inevaluability" are study-specific and should be clearly defined in each protocol (depending on treatment duration and treatment periodicity). In some circumstances it may be difficult to distinguish residual disease from normal tissue. When the evaluation of CR depends upon this determination, it is recommended that the residual lesion be investigated (fine needle aspiration/biopsy) before confirming the CR status.

Best Overall Response When Confirmation of CR or PR Are Required

When confirmation of response is required, CRs or PRs may be claimed only if the criteria for each are met at a subsequent time point as specified in the protocol (generally 4 weeks later).

Overall Response First Time Point	Overall Response Subsequent Time Point	BOR
CR	CR	CR
CR	PR	SD, PD, or PR ^a
CR	SD	SD provided minimum criteria for SD duration met, otherwise PD
CR	PD	SD provided minimum criteria for SD duration met, otherwise PD
CR	NE	SD provided minimum criteria for SD duration met, otherwise NE
PR	CR	PR
PR	PR	PR
PR	SD	SD
PR	PD	SD provided minimum criteria for SD duration met, otherwise PD
PR	NE	SD provided minimum criteria for SD duration met, otherwise NE
NE	NE	NE

Confirmation of CR and PR

Abbreviations: BOR = best overall response; CR = complete response; NE = not evaluable; PD = progressive disease; PR = partial response; SD = stable disease.

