iPFS is defined as the time from date of first dose of study drug to date of iCPD per iRECIST as assessed by Investigator or death, whichever occurs first. Censoring rules are detailed in Table 1b.

Table 1a: Censoring Rules for the PFS/DOR

Situation	Outcome	Date	Event Description/ Censoring Reason
PD per RECIST v1.1 on/before new anticancer therapy or data cutoff date, whichever is earlier	Event	Earliest date of tumor assessment documenting PD	PD per RECIST v1.1
Death without PD per RECIST v1.1 and not receiving new anticancer therapy on/before data cutoff date	Event	Date of death	Death without PD per RECIST v1.1
[PFS only] Subjects with no post-baseline assessments	Censored	Date of First Dose of Study Drug	No Adequate Disease Assessment per RECIST v1.1
No PD per RECIST v1.1 or Death as of data cutoff date and subject not received new anticancer therapy or received it after the data cutoff date	Censored	Date of last disease assessment on/before data cutoff date	Alive without Documented PD
No PD per RECIST v1.1 or Death as of data cutoff date and new anticancer therapy started before the data cutoff date	Censored	Date of last disease assessment prior to new anticancer therapy	Subsequent Anti-cancer Therapy without Documented PD
PD per RECIST v1.1 or Death after new anticancer therapy and the new anticancer started before data cutoff date	Censored	Date of last disease assessment prior to new anticancer therapy	Documented PD or Death after Subsequent Anti-cancer Therapy
PD per RECIST v1.1 or Death after new anticancer therapy and the new anticancer started after data cutoff date	Censored	Date of last disease assessment on/before data cutoff date	Documented PD or Death after Subsequent Anti-cancer Therapy
PD per RECIST v1.1 or Death immediately following two or more consecutive disease assessments missed since the last adequate disease assessment	Censored	Date of last adequate tumor assessment prior to missing assessments	PD or Death after Missing >= 2 Consecutive Disease Assessments
Withdrew consent or lost to follow- up before PD per RECIST v1.1 or Death	Censored	Date of last adequate disease assessment	Discontinued from Study without Documented PD or Death

Regeneron Pharmaceuticals Inc. / Protocol: CMP-001-010 IQVIA Biotech (Confidential) Project # RZA44091

Table 1b: Censoring Rules for the iPFS/iDOR

Situation	Outcome	Date	Event Description/ Censoring Reason

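### Subjects taken off treatment for Investigator-called progression have no scheduled scans afterwards, and the SAP censors them unless BICR has read PD, which biases BICR PFS and DOR event-free rates upward

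*Protocol*

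**What the plan says.** **Endpoints.** PFS and DOR are secondary endpoints, defined by RECIST v1.1 progression as read by BICR (Protocol 2.2.2; SAP V.B).

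**Stopping treatment.** One listed reason in Protocol 4.5 is "Clinical disease progression in the opinion of the Investigator". It needs no RECIST PD.

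**Scans after treatment.** Protocol 4.5 gives posttreatment disease assessments to "Subjects who discontinue study treatment for reasons other than disease progression (either per RECIST v1.1, iRECIST, or clinical PD per Investigator"). Table 1 footnote c likewise limits posttreatment follow-up imaging to subjects who stop for "reasons other than disease progression (either per RECIST v1.1, iRECIST, or clinical PD per Investigator) but have not met criteria for study discontinuation". Protocol 7.8 adds: "Posttreatment follow-up disease assessments will continue until disease progression, initiation of another cancer treatment". It does not say whose progression call is meant. Protocol 3.1 reads more broadly: "Subjects who are posttreatment but have not met criteria for study discontinuation should remain on study for posttreatment follow-up (PTFU") and long-term survival follow-up. Progression is not a study-discontinuation criterion in 4.6. Appendix D says of symptomatic deterioration: "Every effort should be made to document the objective progression, even after discontinuation of treatment".

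**Analysis.** SAP VIII.A counts PD or death whether or not treatment has stopped. Table 1a counts BICR PD, or death without new therapy, as events. Otherwise it censors at the last disease assessment, or at the last one before new therapy. It also censors "PD per RECIST v1.1 or Death immediately following two or more consecutive disease assessments missed since the last adequate disease assessment". No row covers clinical PD, or Investigator PD without BICR PD.

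**The concern.** The event is read by BICR, but whether scanning continues depends on why the Investigator stopped treatment. The subjects who lose their scheduled scans are those judged to be getting worse. Kaplan-Meier assumes that a subject censored at a given time has the same outlook as those still followed, and here that is unlikely. The bias runs one way: PFS and DOR look longer than they are. In a single-arm study no comparator carries the same bias.

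Two details add to it. First, Table 1a does not say whether assessments that were never scheduled count as missed, so a later death without new therapy could be read as an event or be censored back to the last scan. Second, a subject who stops for progression before any post-baseline assessment has a best response of PD under SAP VIII.A, yet PFS is censored at first dose under Table 1a if no EOT scan exists.

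**Working it through.** **Step 1: follow one subject.** The Investigator stops treatment for clinical PD. Table 1 schedules imaging at EOT. If BICR reads PD there, the subject is an event. If not, 4.5 and footnote c schedule no more scans. Then:
- new therapy starts: censored at the last scan before it, and later PD or death is not counted;
- death without new therapy: an event, unless unscheduled scans are treated as missed;
- alive without new therapy: censored at the last scan, unless an unscheduled or outside scan reaches BICR.

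**Step 2: inputs for the size.** The documents' only design calculation is for ORR (69 subjects, 7% against 20%). It reproduces: rejecting at 10 or more responses has an upper-tail probability of 0.0215 and power of 0.907. It has no bearing on this point. Nothing is stated for PFS, DOR or the frequency of such stops.
- From Table 1 footnote u: scans at W13D1 and every 9 weeks, that is 12, 21, 30, 39 and 48 weeks after first dose. Twelve months is 365.25/7 = 52.2 weeks, so the 12-month rate is the value after the week-48 scan.
- Assumed: exponential time to BICR PD with median *m* of 16, 20 or 26 weeks; a share *q* of 10%, 20% or 30% of BICR progressions lost, each censored at the scan before the one that would have shown PD.

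**Step 3: formula.** Let S_k = 2^(-t_k/m) and h_k = 1 - S_k/S_(k-1). At scan k the risk set is S_(k-1)(1 - q·h_k) and the events are S_(k-1)(1 - q)h_k. The Kaplan-Meier factor is (1 - h_k)/(1 - q·h_k), so

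KM(48) = S(48) / Π(1 - q·h_k),

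which is never below S(48).

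**Step 4: numbers.** For m = 20 and q = 30%: h_1 = 1 - 2^(-12/20) = 0.340 and the other four are 1 - 2^(-9/20) = 0.268. The product is 0.898 × 0.9196^4 = 0.642. S(48) = 0.1895, so KM = 0.1895/0.642 = 29.5%.

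| True median | True 12-month PFS | q = 10% | q = 20% | q = 30% |
|---|---|---|---|---|
| 16 weeks | 12.5% | 14.9% (+2.4) | 17.8% (+5.3) | 21.4% (+8.9) |
| 20 weeks | 18.9% | 21.9% (+2.9) | 25.3% (+6.4) | 29.5% (+10.6) |
| 26 weeks | 27.8% | 31.2% (+3.4) | 35.0% (+7.2) | 39.5% (+11.7) |

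Differences are in points, taken before rounding. If progressions due at the first scan are never lost, the first factor drops out. The m = 20, q = 30% cell becomes 0.1895/0.715 = 26.5% (+7.5), and the whole grid runs from +1.8 to +8.4. Across both versions the range is about 2 to 12 points.

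**Step 5: the median.** It can only fall on a scan date. At m = 16 it is 21 weeks for q = 0, 10% and 20%, and 30 weeks at q = 30%. At m = 20 it moves from 21 to 30 weeks at q = 10% and stays there. At m = 26 it is 30 weeks up to q = 10%, then 39.

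**Step 6: DOR.** Assume a true median of 9 months and scans every 9 weeks from response: h = 1 - 2^(-63/273.9) = 0.147, with five scans by 12 months. The 12-month rate is 45.1% at q = 0, and 48.5%, 52.3% and 56.5% at q = 10%, 20% and 30%. The median is 10.3 (q = 0 and 10%), 12.4 and 14.5 months.

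**Step 7: what pulls it back** (m = 20, q = 30%, all assumed).
- BICR reads PD on the EOT scan in half the group: q acts as 15%, the product is 0.949 × 0.9598^4 = 0.805, KM is 23.5%, and the bias falls from 10.6 to 4.6 points.
- Half die as events within 16 weeks: simulation gives about 5.5 points.
- Half die later, on average 20 weeks after the stop, with first-scan progressors spared: simulation gives 18.8% true, 26.4% without deaths and 25.1% with them.

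**The case against.** The strongest reply is that the gap is narrow.

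- **Scanning does not end at the Investigator's call.** Under Protocol 7.2.4.1, clinically stable subjects with Investigator PD should stay on treatment and be rescanned at least 4 weeks later, with further assessments on schedule. EOT imaging follows. Investigator-only PD will therefore often give BICR another scan. This stands, and it leaves clinical PD as the main group.
- **BICR PD can still be documented after EOT.** Protocol 7.2.1 asks that unscheduled and outside-institution scans be collected for RECIST assessment and sent to BICR. This stands, but such scans are not guaranteed.
- **The protocol conflict is mild.** Section 3.1 sends the reader to Table 1, whose footnote c is specific, and Appendix D is offered as reference text. A reader might infer a flat contradiction. What the text supports is loose wording that needs reconciling.
- **Mitigation is planned.** Investigator-assessed PFS and DOR count Investigator RECIST PD, and SAP VIII.C tabulates censoring reasons. This helps with the smaller group only, because Investigator PFS follows the same Table 1a rules and does not count clinical PD either.
- **Stakes are low.** The SAP makes all analyses descriptive and exploratory with 44 subjects enrolled. The primary endpoint is confirmed ORR, which is not shown to be affected.

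**Conclusion.** The point holds as a minor one. Under 4.5 and footnote c, subjects stopped for Investigator-called progression have no scheduled scans after EOT, and Table 1a censors them unless BICR PD or an eligible death is recorded. That censoring is related to prognosis and raises the BICR PFS and DOR event-free rates.

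The direction follows from the rules; the size does not. The 2 to 12 points at 12 months rest on assumed *q*, assumed exponential medians and loss exactly one scan before BICR PD, and they come before any offset from deaths or EOT reads.

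Two stronger readings are tempting. One is that imaging stops as soon as the Investigator calls progression, so that BICR PD can never be seen; the rescanning, EOT and unscheduled-scan provisions rule that out. The other is that the median is inflated by 1/(1 - q). That describes continuous observation with events removed proportionally. With scans 9 weeks apart the median either stays put or jumps to a later scan date.

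**What to change.** - **SAP VIII.C:** add a supplementary BICR PFS and DOR in which stopping treatment for clinical PD, or for Investigator PD without BICR PD, is an event on the stop date. Show it beside the main estimate and report how many subjects the main analysis censors this way. SAP VII.B already lists clinical progression and RECIST PD as separate discontinuation reasons, so no new data are needed.
- **SAP Table 1a:** state that assessments not scheduled after such a stop are not missed assessments, so a later death without new therapy is an event.
- **Protocol 3.1, 4.5, 7.8, Table 1 footnote c and Appendix D:** reconcile who is scanned after treatment stops and whose progression call ends scanning. Enrollment has closed and SAP II.F ends the study 100 days after the last ongoing subject's last dose, so this has less practical value than the SAP changes, which stand alone.

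The cost is one extra table and a few lines of wording. The supplementary PFS and DOR may look shorter than the main estimates.

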4.6. Study Discontinuation

Subjects may withdraw from the study at any time and without penalty or loss of future medical care, or any other benefits to which they are otherwise entitled. Subjects will be withdrawn from the study for any of the following reasons:

- Subject withdraws consent for the study
- Subject lost to follow-up
- Death
- End of Clinical Trial

Subjects who withdraw consent from overall study participation (not only study treatment) will not have the EOT visit, safety follow-up visits, or further evaluations performed.

4.7. End of Clinical Trial

The End of Clinical Trial is defined as the last visit for the last subject on the study.

5. TREATMENT OF SUBJECTS

5.1. Administration of Study Treatment

5.1.1. Nivolumab

Subjects will receive CMP-001 10 mg IT injection followed by nivolumab 360 mg IV at W1D1 and Q3W thereafter until the subject satisfies a condition for study treatment discontinuation. Nivolumab should be administered to the subject according to the nivolumab Investigator's Brochure. Nivolumab should be administered until the subject satisfies a condition for study treatment discontinuation (Section 4.5.). On visits where both study treatments are administered, nivolumab should be administered after CMP-001. There is no specified waiting period between the end of CMP-001 injection and the initiation of nivolumab infusion.

Participants should receive nivolumab at a dose of 360 mg as a 30-minute infusion each treatment cycle until progression, unacceptable toxicity, withdrawal of consent, or the study ends, whichever occurs first.

There will be no dose escalations or reductions of nivolumab allowed. Participants should be dosed in accordance with the Schedule of Assessments (Table 1).

Participants should be carefully monitored for infusion reactions during nivolumab administration. If an acute infusion reaction is noted, participants should be managed according to Section 5.1.5.

Doses of study treatment(s) may be interrupted, delayed, or discontinued depending on how well the participant tolerates the treatment. Dosing visits are not skipped, only delayed.

The assessment for discontinuation of nivolumab should be made separately from the assessment made for discontinuation of CMP-001. If discontinuation criteria are met for CMP-001 but not for nivolumab, treatment with nivolumab may continue if CMP-001 is discontinued.

Please refer to the current nivolumab Investigator's Brochure and/or Pharmacy Manual for further details regarding storage, preparation, and administration of nivolumab.

Care must be taken to assure sterility of the prepared solution as the product does not contain any antimicrobial preservative or bacteriostatic agent.

